9.1.2. Relationship of Adverse Events to Study Drug

The relationship of AEs to the study drug (not related, related) will be captured on the eCRF.

The TEAEs related to study drug will be summarized by treatment groups as defined in Section 5 and overall, as well as by SOC and PT. If the relationship to study vaccine is missing, then a “missing” relationship category will be included in the summary. A subject with 2 or more AEs within the same SOC or PT level but different relationship will be counted only once in the level using the related incident.

9.1.3. Severity of Adverse Event

The severity of AEs (Grade 1, 2, 3, or 4) will be captured on the eCRF. The TEAEs will be summarized by treatment groups as defined in Section 5 and overall, as well as by SOC, PT, and severity. If the severity is missing, then a “missing” severity category will be

included in the summary. A subject with 2 or more AEs within the same SOC or PT level but different severity will be counted only once in that level using the most severe incident.

9.1.4. Serious Adverse Events

An AE or suspected adverse reaction is considered “serious” (SAE) if, in the view of either the investigator or Sponsor, it results in any of the following outcomes:

- Death
- Life-threatening AE
- Inpatient hospitalization or prolongation of existing hospitalization
- Persistent or significant incapacity or substantial disruption of the ability to conduct normal life functions
- Congenital anomaly or birth defect

Important medical events that may not result in death, be life threatening, or require hospitalization may be considered serious when, based upon appropriate medical judgment, they may jeopardize the subject and may require medical or surgical intervention to prevent one of the outcomes listed in this definition. Examples of such medical events include allergic bronchospasm requiring intensive treatment in an emergency room or at home, blood dyscrasias or convulsions that do not result in inpatient hospitalization, or the development of drug dependency or drug abuse.

An AE or suspected adverse reaction is considered “life threatening” if, in the view of either the investigator or Sponsor, its occurrence places the subject at immediate risk of death. It does not include an AE or suspected adverse reaction that, had it occurred in a more severe form, might have caused death. The investigator must immediately (within 24 hours of awareness) report to the Sponsor any SAE through the agreed upon reporting mechanism.

The SAEs will be presented in a data listing and summarized by treatment groups as defined in Section 5 and overall, as well as by SOC and PT. A subject with 2 or more SAEs within the same level of summarization will be counted only once in that level.

9.1.5. Adverse Events Leading to Withdrawal

The AEs leading to withdrawal will be presented in a data listing.

9.1.6. Adverse Events of Special Interest

Certain AESIs are evaluated after the administration of immunostimulatory agents. All subjects enrolled in the study will be monitored for AESIs from enrollment through the EOS visit. The occurrence of any of these AEs will be treated as an SAE, meeting the criterion of a “medically important event.” The list of AESIs is presented in Section 6.2 of the Protocol. The AESI diagnosis, as well as any medications taken to treat the condition, will be recorded in the subject’s eCRF.

All AESIs will be presented in a data listing.

9.1.7. Solicited Adverse Events

The term “reactogenicity” refers to selected signs and symptoms occurring after dose administration, to be collected by the subject during the day of each dose administration and for the following 7 days using self-reporting and the memory aid.

The following solicited reactogenicity events are included in the memory aid:

Solicited local reactogenicity events:

- injection site induration/swelling
- injection site tenderness
- injection site erythema/redness
- injection site pain

Solicited systemic reactogenicity events:

- body temperature (oral)
- generalized myalgia (muscle ache or pain)
- generalized arthralgia (joint ache or pain)
- headache

- fatigue/malaise (unusual tiredness)
- nausea/vomiting
- diarrhea

The investigator will later review, confirm, grade, and attribute reactogenicity events, as absent (Grade 0), mild (Grade 1), moderate (Grade 2), severe (Grade 3), or potentially life threatening (Grade 4) based on the Toxicity Grading Scale for Healthy Adult and Adolescent Volunteers Enrolled in Preventative Vaccine Clinical Trials (CBER 2007; Table 6-3 in the protocol).

Any solicited reactogenicity event that meets any of the following criteria will be entered as an AE in the AE page in the database:

- Solicited local or systemic reactogenicity event leading to the subject withdrawing from the study or the subject being withdrawn from the study by the investigator
- Solicited local or systemic reactogenicity event lasting beyond 7 days duration
- Solicited local or systemic reactogenicity event that lead to subject withdrawal from study drug
- Solicited local or systemic reactogenicity event that otherwise meets the definition of an SAE

The solicited local and systemic reactogenicity events will be presented in the data listings, and be summarized by treatment as defined in Section 5 and overall, vaccination (first or second), day after vaccination (1-7) and severity. The duration of solicited reactogenicity events will be summarized by treatment as defined in Section 5 and overall, and vaccination (first or second).

The solicited reactogenicity events entered as AEs in the AE eCRF page that are related to study drug will be summarized by treatment groups as defined in Section 5 and overall, as well as by SOC and PT. If the relationship is missing, then a “missing” relationship category will be included in the summary. A subject with 2 or more AEs within the same

SOC or PT level but different relationship will be counted only once in the level using the related incident.

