### **VAL-181388 Administration and Dose Escalation Schema**

VAL-181388 (or placebo) will be administered as an intramuscular (IM) injection (0.5 mL) into the deltoid muscle, preferably in the non-dominant arm, as a 2-dose schedule; the first dose will be given at Visit 1 followed by a second dose 28 days later. VAL-181388 accountability, dose preparation, and administration will be performed by unblinded pharmacy personnel or unblinded designees who will not participate in any other aspect of the study. The remainder of the site staff and all subjects will remain blinded to treatment assignment.

Consent and Screening will occur over a 28-day period prior to randomization. A total of 20 subjects will be randomly assigned to each dose level cohort, 4 subjects (3 VAL-181388 and 1 placebo) to the sentinel safety group and 16 subjects (12 VAL-181388 and 4 placebo) to the expansion group, resulting in 15 subjects being randomly assigned to VAL-181388 and 5 subjects being randomly assigned to placebo (3:1 ratio overall). Subjects meeting all eligibility criteria will receive the first vaccination at Visit 1. Each subject will be monitored in the clinic for at least 1 hour following each vaccination for safety. Assessments will include vital sign measurements and any immediate reactogenicity. Of note, on the day of scheduled vaccination, if a subject is noted to have a systolic or diastolic blood pressure, heart rate, or respiratory rate measurement that shows Grade 2 or higher toxicity after 2 measurements (even after relaxing or resting); has an acute illness; or has an oral temperature  $>38^{\circ}\text{C}$ , the subject should not receive a vaccination on that day and will need to return on subsequent days for their vaccination.

All subjects will return to the clinic at 7 (+3), 17 ( $\pm 3$ ), and 28 (+7) days following each vaccination. In addition, the sentinel safety group will return to the clinic at 1, 2, and 21 (+3) days following the first vaccination. A second vaccination will occur 28 days after the first vaccination (+7 days).

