**Figure 3-1** **Dose Level Schematic**

Abbreviation: SMC, Safety Monitoring Committee.

1. A sentinel safety group of 4 subjects in each cohort will receive VAL-181388 or placebo (3:1) on Day 1.
2. Review of safety subject data by the internal safety team (IST) through at least 7 days after first vaccination (inclusive of reactogenicity, laboratory testing results, and adverse events) is required before the full cohort can be randomized.
3. Safety assessment for dose escalation by the Safety Monitoring Committee (SMC) will occur when all subjects in a dosing cohort have completed their 7-day post second vaccination visit (inclusive of reactogenicity, adverse events, and laboratory results) and will include safety data accumulation through the entire period for that cohort and all previous dosing cohorts.
4. The IST may perform additional reviews of blinded safety data during the active vaccination phase of the study, and will raise concerns to the SMC if there are findings that could affect subject safety.

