### **3.5.2 Completion of Memory Aid**

The memory aid utilized will be a diary card (paper or electronic device) and is a method to record systematic collection of AE information from the subject; this information is subject to potential change based on further questioning and/or follow-up by study staff. Each subject will be instructed to complete a memory aid to describe:

- Solicited local and systemic AEs (Section [3.5.6](#)) occurring (with appropriate documentation to allow severity grading by the investigator) during the day of each dose administration and for the following 7 days
  - Daily oral body temperature measurement is to be performed at approximately the same time each day using the thermometer provided by the study site. If body temperature is taken more than once in a given day, only the highest temperature reading will be recorded.
  - For solicited local AEs that require measurement, the measurement of size will be performed using the ruler provided by the study site.
- All medications (excluding vitamins and minerals) taken during the day of each vaccine administration and for the following 28 days
- Any unsolicited AE during the first 28 days following each vaccination

Study staff will review the information regarding solicited and unsolicited AEs, temperatures, and concomitant medications during the clinic visit. This information will be recorded in the subject's source documents and the eCRF.

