### **3.5.6       Solicited Safety Measurements**

The term “reactogenicity” refers to selected signs and symptoms (AEs) occurring after dose administration, to be collected by the subject during the day of each dose administration and for the following 7 days using self-reporting and the memory aid. Subjects will be instructed to call or return to the clinic within 24 hours if reactogenicity reaches Grade 3 or higher during the first 7 days following vaccination.

The following AEs are included in the memory aid.

Solicited local AEs include:

- injection site induration/swelling
- injection site tenderness
- injection site erythema/redness
- injection site pain

Solicited systemic AEs include:

- body temperature (oral)
- generalized myalgia (muscle ache or pain)
- generalized arthralgia (joint ache or pain)
- headache
- fatigue/malaise (unusual tiredness)

- nausea/vomiting
- diarrhea

The AEs will be recorded by subjects daily using the memory aid; where appropriate reactogenicity measurements will be taken using the tools provided (oral thermometer and measuring device). The investigator will later review, confirm, grade, and attribute AEs including reactogenicity, as absent (Grade 0), mild (Grade 1), moderate (Grade 2), severe (Grade 3), or potentially life threatening (Grade 4). The Toxicity Grading Scale for Healthy Adult and Adolescent Volunteers Enrolled in Preventative Vaccine Clinical Trials ([CBER 2007; Table 6-3](#)) will be used to grade reactogenicity reactions. If a solicited local or systemic AE continues beyond 7 days after dose administration, it will also be recorded as an AE in the eCRF from 8 days after vaccination until resolved or stable.

Other solicited reactions:

Use of analgesics and/or antipyretics will be recorded as absent or present, and it will be indicated if they were used for treatment or for prophylaxis.

Solicited local and systemic AEs (including body temperature) will be collected using the memory aid during the day of each dose administration (at approximately 6 hours) and for the following 7 days. To improve recall for the next visit, subjects will record incidence of unsolicited AEs and medication using the memory aid until approximately 28 days after each vaccine administration.

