For categorical variables, frequencies and percentages will be presented. Continuous variables will be summarized using descriptive statistics (number of subjects, mean, median, standard deviation [SD], minimum, and maximum).

For the summary statistics of all numerical variables unless otherwise specified, minimum and maximum will be displayed to the same level of precision as reported. Mean, median, and confidence intervals (CIs) will be displayed to one level of precision greater than the data collected. Standard deviation will be displayed to two levels of precision greater than the data collected. P-values will be rounded to three decimal places.

When count data are presented, the percentage will be suppressed when the count is zero in order to draw attention to the non-zero counts. A row denoted “Missing” will be included in count tabulations where specified on the shells to account for dropouts and missing values. The denominator for all percentages will be the number of subjects in that treatment within the analysis set of interest, unless otherwise specified.

For the change from Baseline safety summaries, Baseline will be defined as the last non-missing measurement (including repeated and unscheduled assessments) before the first vaccination.

For the immunogenicity analyses, Baseline will be defined as the assessment before the first vaccination.

Study day will be calculated relative to the most recent vaccination. Study day prior to the first vaccination will be calculated as: date of assessment/event – date of first vaccination; study day on or after the date of first vaccination but before the second vaccination (if applicable) will be calculated as: date of assessment/event – date of first vaccination + 1; study day on or after the date of second vaccination will be calculated as: date of assessment/event – date of second vaccination + 1.

Antibody values reported as below the lower limit of quantification (LLOQ) will be replaced by $0.5 \times \text{LLOQ}$. Values that are greater than the upper limit of quantification (ULOQ) will be converted to the ULOQ. Missing results will not be imputed.

All analyses will be conducted using Statistical Analysis System (SAS) Version 9.3 or higher.

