The immunogenicity analyses will be performed separately for the PP sets and the ITT sets. Part A (Visit 1 through Visit 7) immunogenicity data will be included in the analyses for the Primary PP set and the Primary ITT set. Part B (Visit 12 through Visit 19) immunogenicity data will be included in the analyses for the Persistence PP set and the Persistence ITT set.

An exploratory analysis of serum neutralizing antibody titers will be performed using the PRNT80 assay (in addition to PRNT50 assay that used for secondary objectives).

11. Interim Analysis

Following completion of each dose level cohort in Part A, the database will be locked for that cohort and safety and/or immune testing results through 28 days following the final vaccination will be analyzed. As dose escalation occurs, cumulative analyses will be included for each subsequent data lock to allow for all prior dose level cohorts to be analyzed by dose level and in aggregate for VAL-181388 exposure. Also an interim analysis of safety, reactogenicity immunogenicity data collected from Day 1 to Month 7 will be conducted. Immunogenicity and safety data, including analyses of change from

baseline, where applicable, will be summarized for each dose level cohort and combined placebo group. These analyses will be performed by an unblinded team, independent of the study team. Access to individual listings will be restricted to identified Sponsor members and the clinical research organization unblinded team. Study sites will remain blinded. This analysis will provide information regarding short-term antibody persistence.

12. References

Centers for Disease Control and Prevention. Chikungunya virus geographic distribution [updated 22 Apr 2016; cited 2016 Sep 09]. Available from:
<http://www.cdc.gov/chikungunya/geo/index.html>.

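### The by-day severity summary of solicited events covers 7 of the 8 diary days collected after each vaccination, and the SAP does not say which day falls outside it

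*SAP*

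**What the plan says.** **Collection.** SAP 9.1.7 defines reactogenicity as signs and symptoms "to be collected by the subject during the day of each dose administration and for the following 7 days". Protocol 3.5.2 gives the memory-aid window in the same terms ("during the day of each dose administration and for the following 7 days"). Protocol 3.5.6 makes the vaccination-day entry a planned record and counts temperature among the solicited events, which "will be collected using the memory aid during the day of each dose administration (at approximately 6 hours) and for the following 7 days". The clinic also observes subjects for at least an hour after each dose, and the Protocol Synopsis says of this period: "Assessments will include vital sign measurements and any immediate reactogenicity".

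**Summary.** SAP 9.1.7 tabulates solicited events by treatment group and overall, then by "vaccination (first or second), day after vaccination (1-7) and severity". The next sentence summarises duration by treatment and vaccination, with no day range. Protocol 3.6.5.2 asks for reactogenicity by dose level, vaccination, duration, relationship and severity, and sets no day range.

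**Day numbering.** The SAP uses two counts.

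- Section 5 gives a formula: "study day on or after the date of first vaccination but before the second vaccination (if applicable) will be calculated as" the date minus the first vaccination date, plus 1, with the same form after the second dose. The vaccination day is then Day 1. Two other places are consistent with this: SAP Section 11 ("reactogenicity immunogenicity data collected from Day 1 to Month 7 will be conducted") and note 1 to Protocol Figure 3-1, where sentinel subjects "will receive VAL-181388 or placebo (3:1) on Day 1".
- SAP Table 13-1 and Protocol Table 6-1 number the vaccination visit 0. SAP 9.3 follows that count when it places the extra sentinel visits on Days 1 and 2.

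**Endpoint.** Protocol 3.6.1 and SAP 4.2 list solicited events first among the primary safety endpoints, over a seven-day period after each vaccination. Neither says whether the vaccination day is part of that period.

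**The concern.** Within one SAP section, the window in which the data are collected and the range in which they are summarised by grade differ by a day. The section does not say that a day is left out on purpose, or which numbering applies to the table. Two programmers could omit different days and both comply with the text.

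The study tests no hypothesis (SAP 5.1), so for a primary endpoint the descriptive tables are the result. What is at stake depends on the numbering:

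- If the vaccination day is 0, a reaction confined to that day has no entry in the by-day severity summary. A reaction that peaks that day and persists is shown only at its later grades.
- If the vaccination day is 1, the vaccination day is kept, and what is missing is a reaction that starts on the seventh day after dosing.

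**Working it through.** **1. The plan's own count.** The summary levels run from 1 to 7: 7 − 1 + 1 = 7 days per vaccination.

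**2. The collection window.** Count days from the vaccination date, with that date as offset 0. The vaccination day plus the following seven days gives offsets 0 to 7: 7 − 0 + 1 = 8 days. The plan's 7 is not reproduced from its collection rule. It is obtained only if the endpoint wording is read as excluding the vaccination day.

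**3. Which day is outside the range 1–7.**

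| Numbering | Source | Vaccination day | Seventh day after | Outside 1–7 |
|---|---|---|---|---|
| date − vaccination date | Table 13-1, SAP 9.3 | 0 | 7 | vaccination day |
| date − vaccination date + 1 | SAP Section 5 | 1 | 8 | seventh day after |

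One day is outside under either count.

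**4. Size.** The inputs are 60 subjects, with 15 vaccine and 5 placebo recipients per cohort (SAP 5.1), and 2 vaccinations each (SAP 4.1). Complete dosing is assumed.

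- Scheduled diary days: 60 × 2 × 8 = 960.
- Days within the summary: 60 × 2 × 7 = 840.
- Days outside: 960 − 840 = 120, and 120 / 960 = 12.5%.
- Per group of 15 (each dose level, and pooled placebo, 3 × 5 = 15): 15 × 2 × 8 = 240 scheduled and 15 × 2 × 1 = 30 outside.

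These are shares of diary days. The documents give no frequencies of solicited events by day, so they do not convert to a share of events.

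**5. Does other SAP text supply the missing day by grade?**

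- The word overall in the 9.1.7 sentence is attached to treatment groups, as in SAP 9.1.2 to 9.1.4. It most naturally means all groups combined, not all days combined.
- The duration summary has no day limit, so an event on the omitted day can enter it, but without a grade.
- The any-AE and grade 3–4 rows of the overall summary in SAP 9.1.1 count unsolicited events. A solicited event reaches the AE tables only if it meets one of four conditions in 9.1.7: withdrawal from the study, withdrawal from study drug, persistence beyond seven days, or seriousness. A short-lived reaction on the omitted day would normally meet none of them.
- The listings show every record.

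The SAP text therefore has no general graded summary that includes the omitted day.

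**The case against.** The strongest reply is that the table matches the endpoint: seven days after vaccination, tabulated as days 1 to 7 after vaccination. SAP 4.1 also has subjects take their temperature daily for the first seven days after vaccination. This stands in part. The endpoint wording does not settle whether the vaccination day counts, and leaving it out could have been intended. But the SAP does not say so, its own section collects that day, and Protocol 3.5.6 puts temperature in the eight-day window with a timed first entry.

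A second reply is that the list of factors in 9.1.7 need not mean a single cross-tabulation, and that the shells may hold a worst-grade row per vaccination. That is possible. The shells were not available, and the point is made about the SAP text only.

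Three stronger readings are tempting, and the documents do not support them.

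- *That primary-endpoint data are lost.* They are not. Every record stays graded and listed, and safety committee review and the pause rules do not depend on this table.
- *That the vaccination-day peak is what disappears.* This follows only if the vaccination day is 0. Under the Section 5 count that day is retained.
- *That reported severity proportions shift by a calculable number of percentage points.* Leaving out one day changes no proportion shown for the other seven. A shift would arise in a worst-grade summary built from the truncated range, which the SAP text does not specify, and its size would need event frequencies that the documents do not give.

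**Conclusion.** The point holds as a mismatch between collection and tabulation. Followed as written, SAP 9.1.7 gives a by-day severity summary that covers seven of the eight days it collects per vaccination, whichever of the SAP's two numberings is used. With 60 subjects and complete dosing, 120 of 960 scheduled diary days are outside it. The effect on the reported picture of severity is unknown and could be nil.

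The related gap is that the SAP text states no worst-grade summary per vaccination, although Protocol 3.6.5.2 asks for severity by vaccination without a day limit. That part is conditional on the unseen shells.

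The day count is certain; the consequence is limited to the completeness of one descriptive summary. It should be corrected because the summary serves the first-listed primary endpoint and the data are already in hand. It does not call the design or the safety oversight into question.

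**What to change.** Change SAP 9.1.7 only:

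1. State the day numbering for this table and extend it to all eight collected days. Either use Days 0–7, with day = date of record − date of that vaccination, or use Days 1–8 under the Section 5 formula. The two are equivalent.
2. Limit the vaccination-day level to post-dose records, because the schedule of events assesses reactogenicity both before and after dosing.
3. Add a maximum-severity row over the full eight-day window for each vaccination and each solicited term.

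If one day is meant to be left out, the SAP should name it and give the reason.

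The cost is a short SAP edit and an update to the shells: one more day level and one more row per table, from data already collected, with no protocol amendment. The tables become slightly longer. If Days 0–7 is chosen, the labels differ by one from the Section 5 study day, so the table must say which count it uses.
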